**ASSESSMENTS:**

**Efficacy Assessments:** During the double-blind phase, electronic diaries will be completed twice daily by the subject to capture daily nasal symptoms (ie, symptom scores for nasal congestion, nasal discharge [anterior and/or posterior], facial pain or pressure sensation, and sense of smell), and use of approved rescue medication after the Week 4 visit to Week 12. Subject-completed questionnaires will be used to measure the symptoms and social/emotional consequences of the subject's nasal disorder (SNOT- 22), health-related quality of life (EuroQol-5 D [EQ-5D] SF-36v2, and Short Form-6 dimension [SF-6D]), sleep quality and disturbances (Pittsburgh Sleep Quality Index [PSQI]), depressive symptoms (Quick Inventory of Depressive Symptomatology [QIDS]), work productivity, and objective smell test (Smell Identification Test [SIT]). Subjects will assess their global impression of change since starting the study drug using the Patient Global Impression of Change (PGIC) scale. Health economic information related to CRS will also be collected using the Health and Work Performance Questionnaire (HPQ). Objective changes in disease severity will be assessed via sinus CT scan and nasal polyp grading.

**Safety Assessments:** Safety will be assessed by monitoring of AEs throughout the study, nasal examination, vital signs measurements (ie, blood pressure, pulse), weight, and through collection of information for concomitant medications.

**ENDPOINTS:**

**Efficacy**

**Primary:**

**Co-Primary Endpoints:**

- change from baseline to the end of Week 4 in average instantaneous morning (AM) scores (evaluation of symptom severity immediately preceding the time of scoring) of:
  - nasal congestion
  - nasal discharge (anterior and/or posterior)
  - facial pain/pressure sensation

The baseline CSNS is the average of the total instantaneous AM scores over the last 7 days of the single-blind run-in period, and at the end of Week 4, scores are averaged over 7 days before Week 4.

- change from baseline to Week 24/ET in the APOV in the ethmoid and maxillary sinuses

**Key Secondary Endpoints:**

- change from baseline to Week 4 on CSNS score in subjects from studies OPN-FLU-CS-3205 and OPN-FLU-CS-3206 who were symptomatic at trial entry despite reported use of an intranasal steroid for treatment of CRS within 30 days of Visit 1 from studies OPN-FLU-CS-3205 and OPN-FLU-CS-3206
- frequency of acute exacerbations of CRS over the 24-week treatment period, defined as a worsening of symptoms that requires escalation of treatment, from studies OPN-FLU-CS-3205 and OPN-FLU-CS-3206

**Safety Endpoints:**

- monitoring AEs throughout the study; results of nasal examination, vital signs measurements (ie, blood pressure, pulse), and weight; and monitoring concomitant medication usage

**DURATION OF THE STUDY:**

The duration of each subject's enrollment is expected to be approximately 26 weeks.

**STATISTICAL ANALYSIS:**

**Sample Size Determination:** Sample size requirements were based on previous Phase 3 studies of OPN-375 in subjects with nasal polyposis and data from a study evaluating the change in maxillary and ethmoid opacification in CRS patients treated with an intramuscular dose of triamcinolone. Based on the results for changes from baseline in morning symptoms among subjects with nasal polyps in the previous studies conducted with OPN-375, a sample of 111 subjects/group (333 total subjects) is sufficient to detect a 0.8 scale difference in morning symptoms score between treatments (OPN-375 vs placebo) using a 2-sided test at the 5% significance level with 88% power, and assuming a standard deviation (SD) of 1.9. This sample size is also adequate to detect an 11.3% difference between treatment groups in average percent opacification using a 2-sided test at the 5% significance level with 88% power, and assuming a SD of 27%. Approximately 333 subjects will be randomized (111 subjects/group) to have at least 120 subjects without nasal polyps be included.

**Primary Efficacy Analysis:** For the co-primary endpoint CSNS, the estimator is the mean difference between treatments (active versus placebo) in change from baseline to the end of Week 4 in the 7-day average total instantaneous AM CSNS. Estimation is based on a mixed model for repeated measures (MMRM) where changes from baseline to Week 2 and Week 4 in the 7-day average total instantaneous AM CSNS, respectively, are the repeated measures. For the co-primary endpoint APOV, the estimator is the mean difference between treatments (active versus placebo) in the change from baseline to Week 24/ET APOV. Estimation is based on an ANCOVA model including categorical effects for previous sinus surgery (Y,N), nasal polyp status (present, absent), treatment (OPN-375 186 µg, OPN-375 372 µg, placebo), and baseline APOV.

**Key Secondary Efficacy Analysis:**

Change from baseline to Week 4 on CSNS score in subjects who were symptomatic at trial entry despite reported use of an intranasal steroid for treatment of CRS within 30 days of Visit 1 will be analyzed using the same MMRM model described for the co-primary endpoint CSNS, and the model will include a categorical effect term for protocol (CS-3205, CS-3206).

The frequency of acute sinus exacerbations over 24 weeks will be compared between OPN-375 dose groups and placebo using generalized linear model (GLM) for data from the negative binomial distribution that is commonly referred to as the negative binomial (NB) regression model. The NB model will include the same model terms as the primary models; in addition, the model will include a categorical effect for protocol (CS-3205, CS-3206), and the logarithm of follow-up time as an offset variable.

**Safety Analysis:**

All safety summaries will be descriptive; no statistical inference procedures will be applied. All safety summaries will be presented by OPN-375 dose level (186 µg and 372 µg) and total OPN-375, and placebo.

## SCHEDULE OF STUDY PROCEDURES AND EVALUATIONS

Period	Pretreatment (Screening/ Run-in)	Double-blind Treatment						
	1	2	3	4	5	Subject Contact	6**	
Procedures and assessments	Single-blind Placebo Run-in (-7 up to -21 days)	Baseline (Randomization) Day 1	Week 4 a ±7 days	Week 8 a ±7 days	Week 12 a ±7 days	Week 16 ±7 days	Week 20 ±7 days	Week 24 a /ET ±7 days
Informed consent	X							
Demographics	X							
Medical/surgical/smoking history	X							
Inclusion and exclusion criteria	X	X						
Confirm ability to use EDS b	X							
Serum chemistry, hematology, urinalysis	X							
Urine drug screen	X							
Blood Sample for SARS-CoV-2 Serology Testing j								X
Brief physical examination	X							
Urine pregnancy test c	X	X	X	X	X			X
Vital signs and weight	X	X	X	X	X			X
Nasal and sinus endoscopic assessment	X							
CRS treatment and history	X							
Nasal examination d	X							X
Nasal polyp grading	X							X
CT with Lund-Mackay scoring	X e							X f
Exacerbation assessment			X	X	X	X	X	X
Surgical intervention assessment		X						X
SNOT-22		X	X	X	X			X
EQ-5D		X						X
SF-36v2		X						X
PSQI		X			X			X
QIDS		X						X
HPQ		X	X	X	X			X
SIT		X						X
PGIC			X					X
Dispense/collect study drug (OPN-375)	X g	X	X	X	X			X
Review proper use of EDS	X	X	X	X	X			
Treatment compliance		X	X	X	X	X	X	X
Provide/collect subject diary	X				X			

Period	Pretreatment (Screening/ Run-in)	Double-blind Treatment						
		1	2	3	4	5	Subject Contact	6**
Procedures and assessments	Single-blind Placebo Run-in (-7 up to -21 days)	Baseline (Randomization) Day 1	Week 4 a ±7 days	Week 8 a ±7 days	Week 12 a ±7 days	Week 16 ±7 days	Week 20 ±7 days	Week 24 a /ET ±7 days
Review subject's diary entries		X	X	X				
Contact IWRS h	X	X	X	X	X			X
AE collection i	X	X	X	X	X	X	X	X
Prior/concomitant medication/procedures/nondrug therapy	X	X	X	X	X	X	X	X
Contact with subject						X	X	

AE=adverse event; CRF=case report form; DB=double-blind; EDS=Exhalation Delivery System; EOS=End of Study, ET=early termination; HPQ=Health and Work Performance Questionnaire; IWRS=interactive web response system; PGIC=Patient Global Impression of Change; EQ-5D=EuroQol-5; SF-36v2=36-Item Short Form Health Survey version 2; SNOT-22=Sinonasal Outcome Test – 22; PSQI = Pittsburgh Sleep Quality Index; QIDS = Quick Inventory of Depressive Symptomatology, SIT = Smell Identification Test.

\*\*If subject cannot complete EOS CT scan at the Week 24 visit, subject should continue treatment until an EOS CT scan can be completed. If subject continues treatment:

- Complete Subject Contacts approximately every 4 weeks to assess safety until subject can complete the EOS CT scan
- When EOS CT scan has been completed and subject returns to study site, perform additional SNOT-22, and urine pregnancy test (women of childbearing potential only)

a All visits up to Visit 6 (Week 24) should be scheduled based on the date of the Day 1 visit. If necessary, visits may be performed within the time window shown; however, subsequent visits should be scheduled based on the date of the Day 1 visit.

b The assignment of a kit number for the demonstrator model EDS is not performed by IWRS, rather, the study staff will dispense a demonstrator model EDS kit and record the kit number in the drug dispensing log. This practice EDS is only used at the site at Visit 1 (Screening) and is not to be sent home with the subject.

c Women of child-bearing potential only; urine pregnancy tests will be performed at each visit, not including subject contacts. Subjects continuing treatment past Week 24/Visit 6 will need an additional pregnancy test completed upon returning to site.

d Nasoendoscopy will be performed using a rigid or flexible endoscope. The examiner must be able to visualize the middle meatus with the scope. Decongestants and/or local anesthetics may be used for the nasoendoscopic procedure.

e The CT scan should be performed after diary eligibility is confirmed and prior to Day 21 of the screening run in period.

f For the Week 24 study visit, the CT examination should be performed prior to the on-site visit.

g Demonstrator model EDS kit (see footnote b) and single-blind placebo dispensation only.

h At Visit 1 (Screening), the IWRS will be contacted to obtain the subject ID number, the identifier for the single-blind kit to be dispensed and to track enrollment. IWRS will be contacted at Visit 2 to randomly assign subjects to treatment. At Visit 2 through – Visit 5, IWRS will be used to assign the study drug kit(s) to be dispensed. If a subject cannot complete the EOS CT scan at Visit 6 (Week 24), study staff should not complete Visit 6 in IWRS. Subjects should continue study treatment until an EOS CT scan can be completed. Study staff will dispense additional study medication via the “Unscheduled Visit” functionality in IWRS. IWRS will be contacted for each ‘Unscheduled Visit,’ at which time one treatment kit will be dispensed.

i The period of observation for collection of AEs extends from the time the subject gives informed consent until completion of the double-blind treatment period or an early termination visit. Serious adverse events will be reported through 30 days after the last dose of study drug administration.

j Blood sample for SARS-CoV-2 serology test at Visit 6 should be completed unless the subject declines testing.

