## 6 VISIT SCHEDULE SUMMARY

Procedures to be performed at each study visit, and the visit time windows, are indicated in the [Schedule of Study Procedures and Evaluations](#). Additional information related to the individual study visits is presented below:

- CT scans are required at Baseline and Week 24/ET to evaluate eligibility criteria and primary and secondary endpoints. All CT scans will be sent to a central imaging core lab for review and analysis. The baseline CT scan should be performed after all other screening assessments are completed for subjects who remain eligible (unless utilizing CT scan performed within 14-days prior to Visit 1).
- Subjects who develop an acute upper respiratory tract infection, acute sinusitis, influenza or SARS CoV-2 (COVID-19) during the study must be symptom free for at least 28 days prior to undergoing the Week 24/EOS CT scan. Subjects should continue treatment with study medication until EOS CT scan can be completed.
- For the Week 24 study visit, if the nasal examination or CT scan cannot be performed on the same day as the study visit, they should be performed *before the on site study visit*.

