#### **6.4 Subject Contact (Week 16 and Week 20)**

Subjects will be contacted at Weeks 16 and 20 (approximately every 4 weeks after Visit 5 (Week 12) and before Visit 6 (Week 24) to obtain information on treatment compliance, exacerbation assessment, AEs, and concomitant medications.

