#### **6.5 Visit 6 (Week 24 End-of-Double-blind/Early Termination)**

Subjects who complete the 24-week double-blind treatment phase, and those who prematurely withdraw from the study for any other reason during this phase should return to the study site and have the end-of-study/ET from study visit performed, including a CT scan. If a subject could not complete EOS CT scan at the Week 24 visit, subject should have all other scheduled procedures performed and continue on study treatment until an EOS CT scan can be completed. Additional Treatment kits can be dispensed via the 'Unscheduled Visit' functionality and the Visit 6 contact should not be completed in IWRS. If subject continues treatment, study staff will complete subject contacts approximately every 4 weeks to assess safety until subject can complete the EOS CT scan. When EOS CT scan has been completed and subject returns to study site, study staff will perform an additional SNOT-22, urine pregnancy test (women of child bearing potential only), and contact IWRS to complete Visit 6.

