**Table 5: Laboratory Measurements**

Hematology	Serum chemistry
– hemoglobin concentration	• sodium
– red blood cell count	• potassium
– mean corpuscular volume (MCV)	• calcium
– white blood cells (total and differential)	• chloride
– platelet count	• urea
– hematocrit	• creatinine
	• total bilirubin
	• alkaline phosphatase
	• alanine transferase (ALT)
	• aspartate transferase (AST)
	• gamma-glutamyltransferase (GGT)
	• albumin
	• total protein
	• glucose
Urinalysis (dipstick)	Urine Drug Screen
• pH	• cocaine
• glucose	• phencyclidine
• protein	• amphetamines class
• ketone bodies	• benzodiazepines class
• indicators of red and white blood cells	• barbiturates class
	• opiates class
	• propoxyphene
	• methaqualone
	• methadone
• Women of child-bearing potential only: A urine pregnancy test will be performed at each visit, not including Subject Contacts. Subjects continuing treatment past Week 24/Visit 6 will need an additional pregnancy test completed upon returning to site.	

At Visit 6/Week 24/ET, a blood sample will be obtained for SARs COV-2 serology testing.

Blood samples and urine drug screens will be analyzed at a central laboratory facility. Urine samples will be analyzed by dipstick and a microscopic analysis will be performed if the results of dipstick indicate abnormalities to be further investigated. All laboratory reports must be reviewed, signed, and dated by the investigator. A legible copy of all reports must be filed with the subject's source documentation.

If any laboratory tests are performed as part of a subject's standard of care after Visit 1 (Screening) and before Visit 2, Day 1 (Baseline), and a change from the Visit 1 (Screening) laboratory test result is considered by the investigator to be clinically significant, the investigator should reassess the subject's eligibility. If any laboratory tests are performed as part of a subject's standard of care after the subject is randomized, and a change from the Visit 1 (Screening) laboratory test result is considered by the investigator to be clinically significant, it should be considered an AE if it meets the definition provided in [Section 8.1](#). Significant abnormal values occurring during the study will be followed until repeat test results return to normal, stabilize, or are no longer clinically significant.

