8.4 Urine Pregnancy Test

For women of childbearing potential, urine pregnancy tests will be performed at the site during every visit. Urine pregnancy test results will be provided in a listing.

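### No protocol text requires a negative pregnancy test before the end-of-study CT scan

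*Protocol*

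**What the plan says.** **Tests.** The Schedule marks a urine pregnancy test at Visits 1 to 6: Screening, Day 1 and Weeks 4, 8, 12 and 24/ET. Footnote c says that, for women of childbearing potential, "urine pregnancy tests will be performed at each visit, not including subject contacts". Protocol Table 5 agrees: "A urine pregnancy test will be performed at each visit, not including Subject Contacts". SAP 8.4 says that "urine pregnancy tests will be performed at the site during every visit". Between Weeks 12 and 24 there are only contacts (Protocol 6.4): "Subjects will be contacted at Weeks 16 and 20". These cover compliance, exacerbations, adverse events and medications. The only stated requirement for a negative result is eligibility at Visit 1 (Protocol 4.1, criterion 3).

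**Timing of the Week 24 CT.** Footnote f reads: "For the Week 24 study visit, the CT examination should be performed prior to the on-site visit". The SAP repeats it under Table 3.1. Section 6, third bullet, deals with the case where the "CT scan cannot be performed on the same day as the study visit", and then asks for it before the on-site visit. A same-day scan is therefore allowed, with an earlier day as the fallback.

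**Delayed CT.** After an acute respiratory infection or sinusitis, a subject "must be symptom free for at least 28 days prior to undergoing the Week 24/EOS CT scan". Section 6.5 says: "If a subject could not complete EOS CT scan at the Week 24 visit, subject should have all other scheduled procedures performed". The Week 24 test is therefore still done. The ** note and 6.5 then place an additional test at the return to site once the scan is complete.

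**Pregnancy during the study.** Section 4.3 requires withdrawal from treatment and strongly encourages subjects who stop treatment to stay for all scheduled procedures. It does not mention the CT.

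**The concern.** Attachment 2 names CT radiation as a risk to subjects. The trial already plans and pays for a urine test at Week 24, but the text does not ensure that its result is known before the Week 24 scan. Where the scan is on an earlier day and the test waits for the visit, the result comes too late to be used. For delayed scans, the one test that the text adds comes after the exposure.

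Section 4.3 leaves a related gap. A subject who becomes pregnant stops treatment but is encouraged to complete scheduled procedures, which include the end-of-study CT, and no exemption is written down.

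What is at stake is avoidable radiation exposure in an unrecognised or known pregnancy. No endpoint, model or error rate is involved.

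**Working it through.** **Inputs**
- Nominal days, SAP Table 9.2: Week 12 = Day 84, Week 24/ET = Day 168. These reproduce as 12 × 7 = 84 and 24 × 7 = 168.
- Visit windows, Schedule: ±7 days at both visits.
- Lead time L from an earlier-day CT to the on-site visit: not given. I assume 1 to 7 days.
- Supply: 3 kits at Week 12 (Protocol 5.1); 2 units per kit and 120 sprays per unit (5.3); 1 spray per nostril from each unit, twice daily (5.1).

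**Case 1: on-time CT on an earlier day, Week 24 test at the on-site visit**
- Gap from the Week 12 test = 168 − 84 − L = 84 − L days. For L = 1 to 7 this is 83 down to 77 days.
- Shortest spacing: (168 − 7) − (84 + 7) = 70, less L. With L = 7 this is 63 days.
- Longest spacing: (168 + 7) − (84 − 7) = 98, less L. With L = 1 this is 97 days.
- Supply: each unit gives 2 sprays per dose × 2 doses = 4 sprays a day, so 120 / 4 = 30 days per kit and 3 × 30 = 90 days from Week 12. At nominal spacing (84 days) no dispensing visit is needed in between. Gaps above about 90 days would outlast those kits and might involve an extra dispensing visit, at which a test could be done. The top of the range is therefore less secure than the nominal figure.

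**Case 2: on-time CT on the visit day**
- The gap is 0 days if the test is done first. Section 6 does not set the order of test and scan.

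**Case 3: delayed CT**
- The gap runs from the Week 24 test and equals the delay. If infection symptoms are still present at the Week 24 visit, the symptom-free rule makes it at least 28 days.
- Extra kits are dispensed one per unscheduled visit, so about every 30 days. If the each-visit rule includes those visits, tests recur at that interval. The text does not say whether it does, and otherwise no maximum gap is set.

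**Case 4: early-termination CT**
- If the test is not done before the scan, the gap depends on the last visit attended, and again no order is set.

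The documents give no number of women of childbearing potential, pregnancy rate or fetal dose, so an expected number of exposed pregnancies cannot be calculated.

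**The case against.** The strongest objection is that the order is unspecified, not wrong. Footnote c and Table 5 tie the test to each visit and do not say that it must be done at the site; the version history for 3.0 records that on-site wording was taken out of this rule. The CT and the test both sit under Visit 6, and footnote f puts the CT before the on-site visit, not before the test. Only SAP 8.4, which describes a listing, says at the site. This stands. A reader might infer that the Week 24 test can never inform an earlier-day scan, but the documents do not support that: nothing bars an earlier test, and nothing requires one.

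Second, the earlier-day scan is the fallback in Section 6, and neither its frequency nor its lead time is known. This also stands, so the 84-day figure describes one case and is not a typical gap.

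Third, a reader might infer from 6.5 that pregnant subjects are told to have an early-termination CT. That sentence concerns subjects who withdraw from the study, whereas 4.3 lists pregnancy as a reason to stop treatment. The supportable point is narrower: 4.3 encourages completion of scheduled procedures and states no exemption.

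Fourth, CT standards are delegated to an Imaging Charter that is not among the documents, and local radiology departments may screen. The conclusion is therefore limited to the visible protocol text. A multicentre protocol should still not depend on site practice that it does not state.

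Finally, clinical sequencing belongs in the protocol. The SAP copies the schedule and lists results, so it is not where the problem lies.

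**Conclusion.** The point holds in a limited form. The visible protocol does not require a negative pregnancy test before the end-of-study CT. In the fallback case, with the CT on an earlier day and the test left to the visit, the last scheduled test is nominally 84 days before Week 24, less the unstated lead time: 77 to 83 days if L is 1 to 7 days. Across the windows the gap is 70 to 98 days less L, with the supply caveat above about 90 days. For a delayed scan the Week 24 test is the last one clearly required beforehand, and it ages by the length of the delay.

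Absolute risk is low. Criterion 2 of Section 4.1 requires women of childbearing potential to be abstinent or, if sexually active, to use effective contraception throughout the study, and Attachment 2 puts the scan at 2.0 mSv.

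A reader might also infer that the plan protects the baseline scan better than the final one. I draw no such comparison: the baseline order serves eligibility, and a routine-care CT from the two weeks before Visit 1 may be accepted.

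This is a cheap improvement of minor priority. It does not affect the efficacy conclusions.

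**What to change.** Change the protocol only; any SAP edit is for consistency.

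- **Footnote f and Section 6, third bullet:** for women of childbearing potential, the Week 24/ET urine test is done and recorded as negative before the CT. On the same day, the test comes first. If the CT is on an earlier day, the test is done at or before the imaging appointment.
- **The ** note and Section 6.5:** require a negative urine test before a delayed CT, and keep the return-visit test as the check at the end of exposure.
- **Section 4.3:** no study CT is done if a test is positive or pregnancy is known.

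The on-time change only reorders a test already planned. The costs are one extra dipstick per delayed scan, some logistics when imaging is on an earlier day (including who records the result), and a missing Week 24 APOV for any subject who tests positive. If the Imaging Charter already imposes this check, a cross-reference to it in footnote f and the ** note would cover the scans, leaving only the sentence in 4.3 to add.
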